**ix. Study Measurements and Protocol**

**Visit 1 (Baseline):**

***Survey 1 (Baseline, 20 min):***

Once written consent has been obtained, a study coordinator will use the REDCap randomization module to assign the participant to a study arm. All participants, regardless of randomization, will receive a baseline survey that they can complete asynchronously in-person (on paper) or via REDCap (an online, HIPAA-compliant data collection tool that can be sent via email). The baseline survey will contain questions about participant demographics (22 questions), threat perception (Threat Perception Survey, 7 questions), uncertainty intolerance (Intolerance of Uncertainty Scale, 27 questions), illness uncertainty (Mishel Uncertainty in Illness Scale for Family Members, 31 questions), PTSS (PCL-5, 20 questions), and the surrogate’s presence during their loved one’s cardiac arrest (4 questions).

**Between Visits 1 and 2:**

***Heartsight Intervention Package 1 (Understanding Cardiac Arrest):***

After completion of the baseline survey, participants assigned to the intervention arm will be emailed login and access details for their Heartsight account. These participants will be instructed to view the Understanding Cardiac Arrest package of articles, which provides information about cardiac arrest and the ICU, and provide article-specific feedback by leaving comments on the website. Participant utilization of Heartsight will be tracked using User Insights. Intervention arm participants who do not access Heartsight within 4 days of receiving access details will be sent a reminder email.

Participants assigned to the control arm will not receive any materials.

***Heartsight Intervention Package 2 (Preparing for Discharge):***

Study coordinators will monitor EPIC to determine when intervention arm participants have moved to the floor. At this time, intervention arm participants will be emailed access details for the Preparing for Discharge package of Heartsight articles, which provides information about getting ready to leave the hospital. They will also be asked to leave article-specific feedback by leaving comments on the website. Participant utilization of Heartsight will be tracked using User Insights. Intervention arm participants who do not access Heartsight within 4 days of receiving Preparing for Discharge access details will be sent a reminder email.

Participants assigned to the control arm will not receive any materials.

### **Visit 2 (Discharge):**

#### ***Survey 2 (Discharge, 15 min):***

Study coordinators will monitor the electronic medical record to determine when participants will be discharged from the hospital. Approximately one day before discharge, study coordinators will approach participants to deliver the second survey. This survey, taken by participants in both arms, can be completed asynchronously in-person (on paper) or via REDCap (online). The discharge survey will contain questions about subjective perception of uncertainty (3 questions), illness uncertainty (Mishel Uncertainty in Illness Scale for Family Members, 31 questions), PTSS (PCL-5, 20 questions), cardiac anxiety (Cardiac Anxiety Questionnaire fear subscale, 8 questions), and social support (Enriched Social Support Instrument, 6 questions). Intervention arm participants who have been identified as viewing less than 25% of the Preparing for Discharge articles will receive two additional questions asking for user feedback.

Upon completion of the discharge survey, study coordinators will process the first \$50 payment to the participant. At this time, study coordinators will also provide all participants with a GENEActiv device, study log, stamped envelope for return, and instructions for proper use and return in 1 week.

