Uncertainty is not equivalent to mere ignorance; rather, a subjective experience of ignorance is a promising target mechanism that may underlie the success of informational interventions for improving the surrogate's cardiac anxiety, PTSS, and sleep. Illness uncertainty contributes to greater psychological distress and poor quality of life outcomes in chronic illnesses, e.g., chronic liver, lung, and heart disease, cancer, and more recently, after COVID-19. Appraisal theories of emotion have specified a direct relationship between uncertainty and emotions. **Uncertainty is also modifiable.** Informational programs may limit uncertainty and improve psychological profiles in cancer survivorship. Despite the surrogate's clear desire for information and high

levels of uncertainty after CA, information-based interventions have never been tested in an acute care setting.

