#### **vii. Study Intervention**

The study intervention for RESURFACE is Heartsight, an online repository of bite-sized, lay-friendly informational articles developed by CA stakeholders for CA surrogates. Heartsight contains three packages of articles developed for specific timepoints in this study. The first two packages aim to reduce illness uncertainty among participants, whereas the third package aims to promote self-care and reduce caregiver burnout:

1. Understanding Cardiac Arrest (15 articles) - articles relevant to understanding CA and the ICU experience; delivered when participants are in the ICU
2. Preparing for Discharge (7 articles) - articles relevant to understanding post-hospitalization life, such as rehab options; delivered when participants are on the floor
3. Focusing on You (12 articles) - articles relevant to practicing self-care after returning home; delivered 3 months after hospital discharge

Study participants will receive unique login and password information for their Heartsight account, created for them by study staff, which will allow the study team to track intervention utilization through User Insights. User Insights enables the study team to track the articles read and time spent per article for each intervention arm participant.

Heartsight is accessible via any device with an internet connection.

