### **Visit 3 (Final):**

#### ***Survey 3 (Final, 20 min):***

Three months after hospital discharge, study coordinators will call participants to schedule the final survey. This survey, taken by all study participants, can be completed via REDCap (online) or over the phone. The final survey will contain

questions about subjective perception of uncertainty (3 questions), illness uncertainty (Mishel Uncertainty in Illness Scale for Family Members, 31 questions), PTSS (PCL-5, 20 questions), cardiac anxiety (Cardiac Anxiety Questionnaire fear subscale, 8 questions), and caregiver burden (Zarit Burden Interview, 12 questions). Intervention arm participants who have been identified as viewing less than 25% of the Focusing on You articles will receive two additional questions asking for user feedback. All intervention arm participants will also receive a Heartsight feedback survey (23 questions).

Upon completion of the final survey, study coordinators will process the final \$50 payment to the participant. At this point, surrogates' participation in the study is considered complete.

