#### **Visit 2 (Discharge):**

##### ***Survey 2 (Discharge, 15 min):***

Study coordinators should check EPIC each morning to determine when participants will be discharged from the hospital. Approximately one day before discharge, study coordinators should approach participants on the floor.

Before approaching, check User Insights to see whether the participant is a low- or no-use participant (accessed <25% of previous Heartsight package). If so, include the low- or no-use questions in addition to the discharge survey in the packet of materials for the participant.

Leave the discharge survey in the correct language (English or Spanish) with the participant to complete. Schedule a time to pick up the completed discharge

survey. At the scheduled time, return to pick up the survey, enter the responses into REDCap, and file the paper survey in the NeuroCardiac Care office.

If the participant has indicated they would prefer to complete the survey on REDCap instead, the study coordinator should click into the “Subjective Discharge” instrument in their REDCap record. If the participant is a low- or no-use participant, click the corresponding radio button, and save. Then click back into the record and switch “Ready to send?” to yes. Save, exit, click back into the record, navigate to “Survey Options,” and open “Survey Access Code + QR Code.” Copy and paste the survey link and code into an email from [[contact]](mailto:[contact]). Confirm verbally with the participant that they have received the email (if not, ask them to check their spam inbox).

The study coordinator should also leave a GENEActiv device, study log, stamped envelope for return, and [instructions for proper use and return in 1 week](#) with the participant. Remind the participant that the study team can be reached at [[contact]](mailto:[contact]) or [contact] if any questions about using or returning the GENEActiv come up.

Once the discharge survey has been completed, study coordinators should also process the first \$50 payment to the participant through TruCentive.

Log dates of discharge survey completion and first payment under [“ALL Participants RESURFACE.”](#)

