**iii. Statistical Methods**

**Statistical approach for Aim 1:** *Enroll up to 100 (until 30 in the intervention arm) surrogates of CA patients to (Aim 1a) pilot recruitment and randomization procedures, (Aim 1b) estimate retention rate at 3 months, and (Aim 1c) assess the engagement and utilization metrics through the app for frequency of access and time spent on packages.*

**Aim 1a.** Based on our prior studies with surrogates of CA patients who survive to hospital discharge, 8 surrogates/month will be eligible to participate in the proposed study and <5 participants/month will be considered not meeting the outcome. **Aim 1b.** Based on our prior successes, we expect retention rates of ~90%. Since this is an

interventional study, the proportion of participants who complete the 3-month assessments <80% will be considered as not meeting the outcome. A sample size of  $N = 30$  surrogates results in a 95% confidence interval of this estimate equal to 79% – 100%, providing sufficient precision for study planning. **Aim 1c.** Acceptability will be assessed by recording reasons for dropout, reasons for noncompliance, and querying participants about burden at 3 months. We will consider scale completion >90% acceptable. The application can track the utilization of the content, time spent on each module of the packages, and participants' review and content feedback.

**Statistical approach for Exploratory Aims 1a-c.** *Estimate the association of intervention v. control with the surrogate's uncertainty levels at 3 months post-discharge (Exploratory Aim 1a), cardiac anxiety, and PTSS at 3 months post-discharge (Exploratory Aim 1b), and explore the lagged associations of uncertainty with cardiac anxiety and PTSS (Exploratory Aim 1c).* We will compute 95% bootstrap confidence intervals around the mean difference in **(1a)** uncertainty in illness total scores; **(1b)** total scores on the cardiac anxiety questionnaire and PCL-5 between intervention and control conditions and **(1c)** the associations between surrogates' uncertainty scores and cardiac anxiety as well as PTSS accounting for enrollment, discharge, and 3 month scores. The lower bounds of these correlations will be used for sample size calculations when planning the larger study to account for uncertainty in small samples.  $N = 30$  has been recommended as sufficient for pilot studies.

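### For surrogates whose patient reaches the floor, skipping the ICU package never triggers the low-use questions, and after a short floor stay the Package 2 flag is read before its own reminder is due

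*Combined protocol and SAP*

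**What the plan says.** Section 3.a.vii describes three packages: "Understanding Cardiac Arrest (15 articles") for the ICU, a 7-article package for the floor, and a 12-article package for home. The first two are the ones aimed at illness uncertainty.

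The low-use questions are described in three places:

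- **Section 3.a.ix, Survey 2 (discharge).** Intervention participants identified as "viewing less than 25% of the Preparing for Discharge articles will receive two additional questions asking for user feedback".
- **Section 3.a.ix, Survey 3 (3 months).** Intervention participants identified as "viewing less than 25% of the Focusing on You articles will receive two additional questions asking for user feedback".
- **Section 3.a.x, Survey 2 (coordinator procedure).** Before the discharge approach, the coordinator checks usage for a "low- or no-use participant (accessed <25% of previous Heartsight package"). The package is not named.

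Package 2 is emailed when the patient's move to the floor is seen in the record. Participants who "do not access Heartsight within 4 days of receiving Preparing for Discharge access details will be sent a reminder email". The discharge survey is delivered about one day before discharge, and usage is checked just before that approach.

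Section 3.a.vi lists identifying low users and seeking their feedback among the retention measures. Section 3.b.iii says for Aim 1c: "Acceptability will be assessed by recording reasons for dropout, reasons for noncompliance", together with a query about burden at 3 months.

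**The concern.** Engagement and acceptability form one of the three parts of the pilot's main aim, and the plan intends to learn why people do not comply. In the survey lists of Section 3.b.i, the no- or low-use questionnaire is the only instrument specific to non-use. It is tied to Package 2 at discharge and Package 3 at 3 months, so the largest package, and the only one delivered in the ICU, has no such trigger for anyone who goes through the floor. Usage logs can show that the ICU articles were skipped. They cannot show why, and the reason cannot be recovered from the logs afterwards.

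Timing is a second issue. The flag has no minimum period of access. If the floor stay is short, a surrogate can be classed as a low user before the plan's own reminder has come due, and a low count may then reflect little time as much as little interest.

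**Working it through.** The plan gives no figure of its own to reproduce here. The check is direct arithmetic on the stated rules.

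**Inputs.** Package sizes 15, 7 and 12 (Section 3.a.vii); flag at under 25% viewed (Sections 3.a.ix and 3.a.x); Package 2 issued on the move to the floor, taken as day 0; reminder after 4 days without access; flag read about 1 day before discharge.

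**1. What the flag means in articles.** The cut-off is the largest whole number k with k/n < 0.25.

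| Package | n | 25% of n | Viewed count below 25% | Low-use questions triggered in the plan? |
|---|---|---|---|---|
| 1 (ICU) | 15 | 3.75 | 0 to 3 | No, if the patient reaches the floor |
| 2 (floor) | 7 | 1.75 | 0 or 1 | Yes, Survey 2 |
| 3 (home) | 12 | 3.00 | 0 to 2 | Yes, Survey 3 |

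For Package 2, 1/7 = 14.3% is flagged and 2/7 = 28.6% is not.

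**2. Share of content without a trigger.** In-hospital articles: 15 + 7 = 22, and 15/22 = 68%. All articles: 15 + 7 + 12 = 34, and 15/34 = 44%.

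**3. Two illustrative surrogates at discharge.**

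- Views 0 of 15 and 2 of 7: (0 + 2)/22 = 9% of in-hospital content. Not flagged.
- Views 15 of 15 and 1 of 7: (15 + 1)/22 = 73%. Flagged.

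These show that the flag can rank in-hospital engagement the wrong way round. They say nothing about how often that happens.

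**4. Flag against reminder.** With a floor stay of L days, the flag is read on about day L − 1 and the reminder is due at day 4. The flag comes first when L − 1 < 4.

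| Floor stay L (days) | Flag read on about day | Relative to the reminder |
|---|---|---|
| 1 | 0 (day of issue) | Before |
| 2 to 4 | 1 to 3 | Before |
| 5 | 4 | Same day |
| 6 or more | 5 or later | After |

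The documents give no distribution of floor stay, so the proportion with L under 5 cannot be computed.

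**5. Different triggers.** The reminder depends on no access at all, the flag on viewing under 25%. A surrogate who opens a single Package 2 article within the 4 days and no more is flagged but not reminded, whatever the length of stay.

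**6. Discharge straight from the ICU.** Package 2 is never issued. Under the Section 3.a.ix wording, 0 of 7 viewed would count as low use of a package never sent. Under the Section 3.a.x wording ("accessed <25% of previous Heartsight package"), the natural referent is Package 1. The two descriptions lead to different actions.

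**The case against.** A reader might infer that non-use of the ICU package goes unexplored. The documents do not support that. Articles read and time per article are tracked for every intervention participant, Package 1 has its own 4-day reminder with dates logged, article comments are invited, and all intervention participants receive a 23-question Heartsight feedback survey at 3 months. Aim 1c's recording of reasons is not limited to particular packages. The feedback items are not in the documents, so nobody can say that they omit Package 1. What stands against this defence is narrower. Tracking does not give reasons, comments come from people who open articles, and the feedback survey comes 3 months after discharge and reaches only those still in follow-up.

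A reader might also infer that every short floor stay is labelled low use. It is not: opening 2 of 7 articles avoids the flag. The wording of the two questions is not given either. If they ask why articles were not viewed, lack of time is an answer they could elicit.

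The link to Aim 1c is an inference. The flag sits under retention, Section 3.b.iii does not mention it, and its only described effect is two extra questions. Nor does the novelty claim, that "information-based interventions have never been tested in an acute care setting", single out the ICU; Package 2 is also delivered during the hospital stay, so in-hospital non-use is partly probed. Finally, a straight-from-ICU discharge is mishandled only if Section 3.a.ix is read without Section 3.a.x.

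All of this limits the consequence. None of it supplies a Package 1 trigger for surrogates who pass through the floor.

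**Conclusion.** The point holds in limited form. For surrogates whose patient reaches the floor, the stated rules mean that non-use of Package 1 never triggers the targeted low-use questions, although Package 1 is 15 of the 22 in-hospital articles. For floor stays under about 5 days, the Package 2 flag is also read before its reminder is due, and at 5 days the two coincide. This assumes prompt issue of Package 2 on transfer and a usage check one day before discharge. It also takes the unnamed package in Section 3.a.x to be Package 2 for anyone who reached the floor.

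The number of surrogates affected is unknown, because neither floor stay nor expected use is given. No estimate, error rate, sample size or Aim 1 success criterion changes. It would go too far to say that the pilot will mislead the design of the larger study. The loss is in what the pilot can learn about why the ICU package was not used. That makes it a worthwhile, inexpensive improvement and not a flaw in validity.

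**What to change.** - **Flag each issued package.** In the Survey 2 text of Sections 3.a.ix and 3.a.x, apply the under-25% rule separately to every package already issued: fewer than 4 of 15 for Package 1 and fewer than 2 of 7 for Package 2. Have the two questions name the package concerned.
- **Reconcile the two sections.** Replace the unnamed previous package in Section 3.a.x with the same per-package rule. Record Package 2 as not issued when the patient never reached the floor, so that the surrogate is not flagged on it.
- **Report exposure time.** In the Aim 1c results, show use of each package alongside the days from its logged issue date to Survey 2, so that low use and short access can be told apart.

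The cost is up to two more questions for some intervention participants and a small change to REDCap and the coordinator procedure. Per-article use, issue dates and discharge-survey dates are already recorded. The protocol lists recruitment as not yet started, so on that status the change can be in place for the first participant.

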### **Between Visits 2 and 3:**

At 1 week post-discharge, study coordinators will call participants to remind them to return the GENEActiv. The second payment of \$25 will be processed once a participant's GENEActiv has been returned to the PACE team.

#### ***Heartsight Intervention Package 3 (Focusing on You):***

One month after hospital discharge, intervention arm participants will be emailed access details for the Focusing on You package of Heartsight articles, which provides information about getting ready to leave the hospital. They will also be asked to leave article-specific feedback by leaving comments on the website. Participant utilization of Heartsight will be tracked using User Insights. Intervention arm participants who do not access Heartsight within one month of receiving Focusing on You access details will be sent a reminder email.

Participants assigned to the control arm will not receive any materials.

### **Visit 3 (Final):**

#### ***Survey 3 (Final, 20 min):***

Three months after hospital discharge, study coordinators will call participants to schedule the final survey. This survey, taken by all study participants, can be completed via REDCap (online) or over the phone. The final survey will contain

questions about subjective perception of uncertainty (3 questions), illness uncertainty (Mishel Uncertainty in Illness Scale for Family Members, 31 questions), PTSS (PCL-5, 20 questions), cardiac anxiety (Cardiac Anxiety Questionnaire fear subscale, 8 questions), and caregiver burden (Zarit Burden Interview, 12 questions). Intervention arm participants who have been identified as viewing less than 25% of the Focusing on You articles will receive two additional questions asking for user feedback. All intervention arm participants will also receive a Heartsight feedback survey (23 questions).

Upon completion of the final survey, study coordinators will process the final \$50 payment to the participant. At this point, surrogates' participation in the study is considered complete.

## **x. Visit Procedures**

### **Visit 1 (Baseline):**

#### ***Survey 1 (Baseline, 20 min):***

Once written consent has been obtained, the study coordinator should leave a baseline survey in the correct language (English or Spanish) with the participant to complete. Schedule a time to pick up the completed baseline survey and explain to the participant that a copy of their completed consent form will be provided to them at that time.

After scheduling the pick-up time, the study coordinator should obtain a patient sticker from the binders near the nursing station. Apply the patient sticker to the consent form, photocopy the consent form, and file the original copy of the consent form in the NeuroCardiac Care office.

The study coordinator should also create a new REDCap record in Arm 3: Randomization. Open “Demographics,” enter the CANOE-F ID, then click the “Randomize” button. If randomized to Heartsight, create a new record with the participant’s CANOE-F ID in Arm 1. If randomized to control, create a new record with the corresponding CANOE-F ID in Arm 2. At this time, also navigate to the “Subjective Discharge” and “Subjective 3-Month” surveys and select “No” for “Ready to send?”. This prevents the discharge and 3-month surveys from automatically joining the survey queue at earlier time points.

At the scheduled time, the study coordinator should return to the ICU, pick up the completed baseline survey, and give the participant the copy of their completed consent form. Enter the completed baseline survey into REDCap and file the paper copy in the NeuroCardiac Care office.

If the participant has indicated they would prefer to complete the survey on REDCap instead, the study coordinator should obtain their email address. Then click into the “Demographics” instrument in their REDCap record, click “Survey

Options,” and open “Survey Access Code + QR Code.” Copy and paste the survey link and code into an email from [[contact]](mailto:[contact]). Confirm verbally with the participant that they have received the email (if not, ask them to check their spam inbox).

The study coordinator should add the participant to the CANOE-F spreadsheet under the “[CURRENT Participants RESURFACE](#)” tab and log date of baseline completion under “[ALL Participants RESURFACE](#).”

